7.2 PARTICIPANT DISCONTINUATION/WITHDRAWAL FROM THE STUDY

Participants are free to withdraw from participation in the study at any time upon written request.

An investigator may discontinue or withdraw a participant from the study for the following reasons:

- Pregnancy
- Significant study intervention non-compliance
- If any clinical adverse event (AE), laboratory abnormality, or other medical condition or situation occurs such that continued participation in the study would not be in the best interest of the participant
- Disease progression which requires discontinuation of the study intervention
- If the participant meets an exclusion criterion (either newly developed or not previously recognized) that precludes further study participation
- Participant is unable to receive buspirone for 7 days.
- The sponsor or investigator terminates the study.

If, during the trial, a participant develops non-life threatening side-effects, the study medication will be suspended if the participant insists, after consultation with a study physician. If the participant decides to stop the study medication, the participant will still be followed in the trial according to the protocol, in keeping with the

intention-to-treat paradigm. In the event of major dermatological reactions such as generalized urticaria, bullous rashes, exfoliative dermatitis, or Stevens-Johnson Syndrome, study drug will be discontinued immediately.

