Treatment of side effects: During BESST, if a participant develops non-life threatening side effects that may be attributed to the study drug, the study drug will be stopped only if the participant so desires. If the participant chooses to no longer receive the study drug, the participant will continue to be followed in the trial, in keeping with the intention-to-treat paradigm. In the event of major dermatological reactions such as generalized urticaria, bullous rashes, exfoliative dermatitis, or Stevens-Johnson Syndrome, study drug will be discontinued immediately. Such skin reactions are expected to be infrequent adverse events.

Study visits: This study requires approximately 8 visits to the study center (up to 3 screening visits, randomization visit, and 4 post randomization visits) which may cause some inconvenience to some individuals.

Pregnancy: Since there may be unknown risks to pregnant women and their unborn children, potential participants who are breast feeding, pregnant, or planning to become pregnant will not be allowed to participate in BESST. Participants need to confirm to the best of their knowledge that they are not pregnant and if they become pregnant during the course of the study, they must notify the study investigator immediately and the study drug will be stopped. A urine pregnancy test is obtained at study enrollment and at each visit during study treatment for any females of child-bearing potential to help assure that the participant is not pregnant.

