7.1 DISCONTINUATION OF STUDY INTERVENTION

If the participant develops a treatment-related CTCAE v5.0-defined adverse event (grade 3 or above) on the 10 mg dose, the study medication will be stopped after assessment by the site study investigator, who is a licensed physician. If in the view of the study investigator, the participant is intolerant of the medication, the participant will be withdrawn from the study medication, but will continue to be followed to the end of the trial.

Discontinuation from buspirone or placebo does not mean discontinuation from the study -- all remaining study data should be completed as indicated by the study protocol. If a clinically significant finding is identified after enrollment, the investigator or qualified designee will determine if any change in participant management is needed. If indicated, adverse event (AE) case report forms will be completed and entered into the study database.

The data to be collected at the time of study intervention discontinuation will include the following:

- Labs and anthropometrics at the prior visit or at the AE occurrence
- Study medication bottle numbers and documentation of capsule counts

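### Section 7.2 permits withdrawal from the study for non-compliance or 7 days off drug, which conflicts with the rule that participants off drug stay in follow-up and could lose week-4 outcomes selectively

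*Combined protocol and SAP*

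**What the plan says.** Section 7.2 opens its list with "An investigator may discontinue or withdraw a participant from the study for the following reasons". Two entries concern exposure to drug: "Significant study intervention non-compliance" and "Participant is unable to receive buspirone for 7 days". The first has no threshold. The list acts on study participation, and it is permissive.

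Other text points the other way:

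- Section 7.1: "Discontinuation from buspirone or placebo does not mean discontinuation from the study -- all remaining study data should be completed as indicated by the study protocol". For intolerance it adds that "the participant will be withdrawn from the study medication, but will continue to be followed to the end of the trial".
- Section 2.3.1, on a participant who chooses to stop because of side effects: "the participant will continue to be followed in the trial, in keeping with the intention-to-treat paradigm".
- Section 7.2, last paragraph, on a participant who decides to stop: "the participant will still be followed in the trial according to the protocol, in keeping with the" intention-to-treat paradigm.
- Section 7, opening paragraph: those who stop drug are to be encouraged to stay, with efficacy outcomes named among the reasons.

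The primary analysis (9.2, 9.3, 9.4.2) covers all randomized participants, with 50 chained-equation imputations for missing week-4 outcomes. Imputation predictors (treatment group and baseline value) are named only for secondary outcomes, in 9.4.3. The sensitivity analyses in 9.4.2 are complete-case, adherence-based, covariate-adjusted, bootstrap if normality fails, item-level, longitudinal (GEE) and diary-based. Section 7.3 expects few missing data, balanced between arms.

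**The concern.** Non-compliance and a week without drug are facts about treatment. They say nothing about whether a participant is willing, or can safely continue, to complete a questionnaire. Making them grounds for leaving the study lets each of six sites decide whether such a participant has a week-4 outcome, and the plan states no rule for that decision.

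At stake is what the primary analysis estimates. Section 9.3 defines it on everyone randomized. If outcomes are missing mainly in people who stopped taking drug, and are imputed largely from people who kept taking it, the estimate moves from the effect of assignment towards the effect in those who stayed on treatment.

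**Working it through.** **1. The rules can meet in one participant.** Someone taken off drug for intolerance in week 1 is to be followed to the end under 7.1. Seven days later the same person can be read as unable to receive buspirone for 7 days, and 7.2 then permits withdrawal from the study. No text settles the conflict.

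**2. Timing.** Treatment lasts 28 days, so a 7-day gap that begins by day 21 is complete before the week-4 visit. Adherence is also reviewed at week 2 (1.3, 8.1.4). A decision before the primary assessment is therefore possible on either ground. Non-compliance found only from the final capsule count is different. Under 8.1.4 the bottles come back at the second week-4 visit, after the visit at which PAGI-SYM is completed, so that route need not cost the outcome.

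**3. Who is affected.** Missing 7 of 28 days leaves at most 21/28 = 75% adherence, below the plan's 80% cutoff (9.3, 9.4.1). Anyone meeting the 7-day ground within the treatment period thus belongs to the low-adherence group, whose week-4 data the comparisons in 9.4.2 and 9.4.7 need.

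**4. Illustrative size.** The plan gives no figure for this, so there is none to reproduce. Inputs:

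- On-drug effect δ = -0.5, the plan's MCID (9.2), taken as the true effect.
- Off-drug share of the buspirone arm p: assumed, 5% to 20%.
- Fraction f of those off drug who are withdrawn before week 4: assumed.
- No benefit kept off drug: assumed.
- Imputation from arm and baseline only, as stated for secondary outcomes: assumed for the primary.

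The placebo off-drug share (5% in the central case) does not enter, because stopping placebo is assumed not to change the mean.

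If everyone is followed, the all-randomized effect is δ(1 - p). If a fraction f is lost, the observed buspirone arm has 1 - p on drug and p(1 - f) off drug, and missing values take the mean of that mix:

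estimate = δ(1 - p)/(1 - pf)

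For p = 15%:

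- all followed: -0.5 × 0.85 = -0.425
- f = 1/3: -0.425/0.95 = -0.447
- f = 1/2: -0.425/0.925 = -0.459
- f = 1: -0.425/0.85 = -0.500

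| p | All followed | f = 1/3 | f = 1/2 | f = 1 |
|---|---|---|---|---|
| 5% | -0.475 | -0.483 | -0.487 | -0.500 |
| 10% | -0.450 | -0.466 | -0.474 | -0.500 |
| 15% | -0.425 | -0.447 | -0.459 | -0.500 |
| 20% | -0.400 | -0.429 | -0.444 | -0.500 |

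A simulation with 54 per arm, SD 0.8 and correlation 0.55, using complete-case ANCOVA in place of imputation, agrees at the extremes. With 15% and 5% off drug it gave -0.424 when all were followed and -0.500 when all those off drug were lost. If half the benefit is kept off drug, the overstatement at f = 1 halves, from 0.075 to 0.038.

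**The case against.** The strongest reply is that follow-up is plainly the default. The 7.2 list says only that an investigator may act, while 7.1, 2.3.1 and the end of 7.2 expressly keep those who stop for intolerance or by choice, the stops most likely to differ between arms. The plan also expects outcomes from low adherers, since it analyses them as a group. This stands as a limit on size: loss is permitted, not required. It does not remove the conflict, because the permission covers the same people and nothing ranks the two rules.

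Four stronger readings are tempting, and the documents do not support them.

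- **Withdrawn participants have no week-4 score and receive on-treatment values.** No section says either. The predictors for the primary imputation are not stated, and the observed data would include those off drug whom sites retain. What stands is that imputing from arm and baseline would not fully correct selection by adherence.
- **The estimate is -0.50 against a true -0.43.** That needs every off-drug participant to be withdrawn, as if 7.1 did not exist. The off-drug rates have no source in the documents.
- **Power suffers materially.** The 10% allowance in 9.2 already covers loss of the primary outcome. A fall to 86.5% at 20% loss uses the change-score SD, 0.8 × √(2 × 0.45) = 0.759. For the planned ANCOVA the residual SD is 0.8 × √(1 - 0.55²) = 0.668, which gives 93.6% with 43.2 per arm. No power claim is made here.
- **The exclusion-criterion entry in 7.2 has the same defect.** It applies only where the criterion rules out further participation in the study, so it is not included.

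**Conclusion.** The conflict is in the text and is certain: 7.2 allows study withdrawal on two grounds that describe drug exposure, while 7.1, 2.3.1 and 7.2's own last paragraph keep participants off drug in follow-up. The consequence is conditional. It arises only if sites use the permission before the week-4 PAGI-SYM is collected.

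The documents do not determine its size. With an on-drug effect of -0.5, 15% versus 5% off drug and no retained benefit, the overstatement is about 0.02 to 0.03 points when a third to a half of those off drug are withdrawn. It is 0.075 points at the limit where all are. These figures also assume that imputation uses only arm and baseline. The effect is modest, but it would run in favour of buspirone under these assumptions, no listed sensitivity analysis would test for it, and it is cheap to prevent.

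**What to change.** Reconcile 7.1 and 7.2. State that significant non-compliance and time off drug, whatever they mean for study drug, do not by themselves end study follow-up. State that the scheduled week-4 PAGI-SYM is still collected from these participants unless they withdraw consent, are lost to contact, or follow-up itself is not in their interest. Leave the other grounds in 7.2 and all decisions on study drug as they stand.

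The cost is a protocol wording change and a few additional questionnaires or visits in participants already enrolled. The sample size of 108 does not change.

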7.3 LOST TO FOLLOW-UP

A participant will be considered lost to follow-up if he or she fails to return for one scheduled visit and is unable to be contacted by the study site staff.

The following actions must be taken if a participant fails to return to the clinic for a required study visit:

- The site will attempt to contact the participant and reschedule the missed visit within 7 days and counsel the participant on the importance of maintaining the assigned visit schedule and ascertain if the participant wishes to and/or should continue in the study.
- Before a participant is deemed lost to follow-up, the investigator or designee will make every effort to regain contact with the participant (where possible, 3 telephone calls and, if necessary, a certified letter to the participant's last known mailing address or local equivalent methods). These contact attempts will be documented in the participant's medical record or private study file, but will not be documented in the study database.
- If the participant cannot be reached, the participant will be considered to have withdrawn from the study with a primary reason of lost to follow-up. All study data collected prior to the lost to follow-up will be used.

The occurrence of missing data in this trial is expected to be low and, when present, is expected to be equally distributed across the 2 treatment groups. We believe, from past experience, that careful selection and education of participants during the screening phase before the consent will result in no more than 10% lost to follow-up before completing the full 4-week treatment period and the 2- week post-treatment follow-up.

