8.1.4 FOLLOW-UP VISITS

Participants will return to the clinical center for follow-up visits at 2 and 4 weeks. A post-treatment washout phase visit will occur at week 6. Each visit will have an interval of time surrounding the ideal date for the visit during which the visit may be done and the data included in the trial database. The ideal date for the week 2 visit is the randomization date plus 2 weeks (14 days); the ideal date for the week 4 visit is the randomization date plus 4 weeks (28 days). Visit windows will be constructed to be contiguous, so that at any point in time, some visit window is open, subject to a check on the minimum separation of at least one week between consecutive visits. The specific assessments and procedures required at each of the follow-up visits are:

- **Week 2:** pregnancy test for females of child bearing potential, follow-up medical history with review of adverse events, concomitant medications and study adherence, assessment of vital signs (systolic and diastolic blood pressure, heart rate, respiratory rate, body temperature), and the following surveys: Hospital anxiety and depression (HADS), PAGI-SYM, and the Clinical Patient Grading Assessment Scale (CPGAS)([see section 8.1.5](#)) and a symptoms side-effect questionnaire (see [section 8.2](#) for details). In addition, the participant will return their Daily-Diary forms and receive another set to complete for return at the Week 4 visit.
- **Week 4:** the week 4 visit will require two fasting visits scheduled as close together as possible, preferably 1 day apart.
 - The participant will refrain from taking their buspirone the morning of the GES test, and take it 30 minutes prior to the GES test. Information to be collected at this visit includes: pregnancy test for females of child-bearing potential, a GES test, follow-up medical history with review of adverse events and concomitant medications, physical exam and ECG, fasting blood draw for CMP and CBC, review of adherence and the following surveys: HADS, SF-36v2 Quality of Life, PAGI-SYM, GSRS, PAGI-QOL, PHQ-15, symptom side-effects, and the CPGAS. Fasting blood will be drawn for serum and plasma banking. In addition, the participant will return their daily-diary forms and receive one more set of daily-diary forms to complete each night to return at their 6-week visit.

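### Section 7.3 lets a participant who misses week 2 and cannot be reached be recorded as withdrawn before the week-4 primary outcome is due, with no earliest date for that status and no route back

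*Combined protocol and SAP*

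**What the plan says.** Section 7.3 joins two conditions. A participant is lost to follow-up who "fails to return for one scheduled visit and is unable to be contacted by the study site staff". After a missed visit, "The site will attempt to contact the participant and reschedule the missed visit within 7 days", and it also asks whether the participant wants to, and should, stay in the study. The status is not automatic: "Before a participant is deemed lost to follow-up, the investigator or designee will make every effort to regain contact with the participant", by three telephone calls where possible and a certified letter if needed. The consequence is then stated: "If the participant cannot be reached, the participant will be considered to have withdrawn from the study with a primary reason of lost to follow-up". Data gathered up to that point are used; the section says nothing about data that might be gathered afterwards. It expects no more than 10% to be lost.

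Section 8.1.4 puts the ideal week-2 and week-4 dates at days 14 and 28 after randomization, and the post-treatment visit at week 6. It adds: "Visit windows will be constructed to be contiguous, so that at any point in time, some visit window is open", subject to at least one week between consecutive visits. The numerical limits of the windows are not given.

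The Schedule of Activities (Section 1.3) collects the PAGI-SYM at screening and at weeks 2, 4 and 6. Study drug is dispensed once, at randomization. The primary analysis (Sections 9.2, 9.4.1 and 9.4.2) is an intention-to-treat ANCOVA in all randomized participants, with multiple imputation of missing week-4 outcomes.

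**The concern.** The trigger is a single visit, and the first visit to which it can apply comes two weeks before the primary outcome. Section 7.3 governs how hard the site must try, but not when it may stop trying. Once a participant is recorded as withdrawn, nothing in the section tells the site to try again at week 4, or says that someone who turns up then may be assessed.

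What is at stake is avoidable loss of the primary outcome. Such a participant has only a baseline PAGI-SYM, so the imputed week-4 value cannot draw on any later score. The sensitivity analyses in Section 9.4.2 (complete cases, adherence subsets, covariate adjustment, single items, the longitudinal model, the diary) do not examine loss that depends on the unobserved outcome. Preventing loss is therefore the main protection the plan has.

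**Working it through.** **Sequence of events under the text**

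1. The participant misses week 2 (ideal day 14). The first condition in Section 7.3 is met.
2. The site tries to reschedule, telephones and, if needed, writes. If the participant is reached and continues, the rule stops there and week 4 remains due. If not, the second condition is met and the participant is considered withdrawn.
3. No earliest date is attached to step 2. The 7 days are a target for rescheduling, not a deadline for declaring loss.

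**When step 2 can fall.** This depends on window limits that the documents do not give, so two assumptions are shown.
- If the 7 days run from the ideal date: 14 + 7 = day 21, a week before day 28.
- If the week-2 window closes midway between the ideal dates, (14 + 28)/2 = day 21, and the 7 days run from there: 21 + 7 = day 28, before allowing time for a letter.

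On the second assumption the week-4 window is already open while the site is still pursuing week 2, because contiguous windows mean one opens as the other closes. On either assumption the status can be assigned while the week-4 visit is still possible.

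**Whether a week-4 score would still be useful.** Missing week 2 does not interrupt drug supply. The bottle issued at randomization holds 120 capsules (Section 6.1.2), and four weeks at three a day need 3 × 28 = 84. A week-4 PAGI-SYM from such a participant belongs in the intention-to-treat analysis in any case.

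**Size.** The planned sample size is reproduced first. Inputs from Section 9.2: SD 0.8, correlation 0.55, difference 0.5, two-sided 5% level, 90% power, 10% allowance.
- SD of change = 0.8 × √(2 × (1 − 0.55)) = 0.759. This is a reading of the sample-size command the protocol names.
- n per group = 2 × (1.960 + 1.282)² × 0.759² / 0.5² = 48.4, rounded up to 49.
- 49 × 1.1 = 53.9, rounded up to 54 per group, or 108 in total. This agrees with the plan.
- Loss allowance: 10% of 108 = 10.8 participants.

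The documents give no rate of missed week-2 visits, failed contact or later recovery. Assume that 3 to 6 participants meet both conditions at week 2, and that between none and half would respond to a fresh approach at week 4. The recoverable outcomes are then 0 to 6 × 0.5 = 3, at most 3/10.8 = 28% of the allowance.

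Power, counting participants with an observed outcome, is Φ(0.5 / (0.759 × √(2/n)) − 1.96):

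| Loss | n per group | Power |
|---|---|---|
| 0% | 54.0 | 92.8% |
| 10% (planned) | 48.6 | 90.1% |
| 10% plus 3 more outcomes | (97.2 − 3)/2 = 47.1 | 89.2% |
| 15% | 45.9 | 88.4% |

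The assumed range moves power by less than one percentage point from the planned level.

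**The case against.** The strongest answer is that the rule is far narrower than its one-visit trigger suggests. A reader might infer that missing week 2 in itself closes the participant. It does not: failure of contact is also required, after prescribed attempts. That objection stands and limits the point to unreachable participants.

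Three further inferences are tempting and are not supported.
- *Closure is due at day 21.* No such deadline is in the text. That date is possible on one assumption about the windows, not required.
- *The rule removes the unwell, the intolerant or those without benefit, and so biases the result.* Sections 7.1 and 7.2 keep participants who stop study drug in follow-up, and the documents say nothing about who becomes unreachable. Informative loss is possible but not shown.
- *Section 7.3 contradicts Section 7.1.* The instruction in 7.1 that "all remaining study data should be completed as indicated by the study protocol" concerns people who stop the drug, not people who cannot be found. The two sections address different cases.

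It is also fair to say that Section 7.3 does not forbid assessing someone who reappears. It is silent, and multiple imputation is in place for whatever is missing. The silence is nevertheless the defect: the only stated outcome is withdrawal, and sites can reasonably treat that as final. For these participants the imputation has no post-baseline PAGI-SYM to use.

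A questionnaire-only remote PAGI-SYM might also be suggested. It is a separate trade-off, because it would introduce a difference in mode of completion into the primary outcome, and it is not part of this point.

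**Conclusion.** The point holds for a participant who misses week 2 and cannot be reached. Section 7.3 allows that person to be recorded as withdrawn before the primary outcome is due, fixes no earliest date and provides no way back, while Section 8.1.4 leaves two later visits available. That participant contributes no post-baseline PAGI-SYM.

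The number affected is probably small and the effect on power slight: about 90.1% to 89.2% over the range considered. Those figures rest on assumed rates of failed contact and recovery and on the reading of the SD of change given above; none of these rates is in the documents. No bias has been demonstrated. This is an inexpensive improvement to a stated rule, not a flaw that threatens the trial's conclusion.

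**What to change.** Amend Section 7.3 as follows:
- Assign lost-to-follow-up status only after the week-6 window has closed without contact.
- After a missed week-2 visit, keep an unreachable participant active and renew contact attempts when the week-4 window opens.
- State that a participant who reappears is assessed at the remaining scheduled visits.

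Participants who themselves ask to withdraw are not affected. The cost is a few sentences of protocol text and a few extra contact attempts for each unreachable participant. The sample size and the analysis do not change.
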